8.3.4. Clinical Safety Laboratory Assessments

See Appendix 2 for the list of clinical safety laboratory tests to be performed and the SoA for the timing and frequency. All protocol-required laboratory assessments, as defined in Appendix 2, must be conducted in accordance with the laboratory manual and the SoA. Unscheduled clinical laboratory measurements may be obtained at any time during the study to assess any perceived safety issues.

The investigator must review the laboratory report, document this review, and record any clinically significant changes occurring during the study in the AE section of the CRF. Clinically significant abnormal laboratory test findings are those that are not associated with the underlying disease, unless judged by the investigator to be more severe than expected for the participant's condition.

All laboratory tests with values considered clinically significant and abnormal during participation in the study or within 5 days after the last dose of study intervention should be repeated until the values return to normal or baseline or are no longer considered clinically significant by the investigator or study medical monitor.

If such values do not return to normal/baseline within a period of time judged reasonable by the investigator, the etiology should be identified and the sponsor notified.

See Appendix 6 for suggested actions and follow-up assessments in the event of potential DILI.

See Appendix 7 for instructions for laboratory testing to monitor kidney function and reporting laboratory test abnormalities.

Participants may undergo random urine drug testing at the discretion of the investigator. Drug testing conducted prior to dosing must be negative for participants to receive study intervention.

8.3.4.1. Fasting Fingerstick Blood Glucose (via Glucometer)

Investigators will monitor fasting FSBG using a glucometer. While the participant is confined to the CRU, FSBG measurements should be taken each morning before breakfast.

FSBG readings will be maintained at the CRU in source documents, and only the glucose results from the laboratory will be reported in the study database. The sites may share the FSBG readings with the sponsor, if necessary for the purpose of safety monitoring, but these data will be stored in the CRU source documents unless related to an AE as described in Section 8.3.4.2.

If an FSBG result is <70 mg/dL

- A **second FSBG** should be obtained to confirm the glucose value this is **in addition to a venous sample** that will be sent to the clinical laboratory for confirmation.
- If the value from this second FSBG is also <70 mg/dL, the **second value** will be recorded as an HAE (see Section 8.3.4.2) and must be captured on the AE CRF, with specific details captured on the HAE CRF.
- FSBG will continue to be monitored until the glucose value returns to ≥70 mg/dL. Samples may be taken more frequently if deemed necessary by the investigator.

FSBG readings from a glucometer are permitted at any time if the investigator or participant notes symptoms of hypoglycemia. Any episode of hypoglycemia must be captured on the AE CRF with specific details captured on the HAE Form CRF.

8.3.4.2. Definition and Severity of Hypoglycemic Adverse Event

The investigator must assess any glucose values, if measured, as well as any signs or symptoms reported by the study participant.

HAE is defined as one of the following:¹³

• Asymptomatic hypoglycemia: An event not accompanied by typical symptoms of HAE but a glucose value of <70 mg/dL (3.9 mmol/L) using either glucometer (fingerstick blood glucose) at the study site or sponsor approved laboratory (plasma glucose).

- Documented symptomatic hypoglycemia: An event during which typical symptoms of HAE are accompanied with a glucose value of <70 mg/dL (3.9 mmol/L), using glucometer (fingerstick blood glucose) at the study site or sponsor approved laboratory (plasma glucose), and the clinical picture includes prompt resolution with food intake, subcutaneous glucagon, or IV glucose.
- Probable symptomatic hypoglycemia: An event during which symptoms of HAE are not accompanied by a glucose determination but was presumably caused by a glucose concentration of <70 mg/dL (3.9 mmol/L), and the clinical picture includes prompt resolution with food intake, subcutaneous glucagon, or IV glucose.

Each episode of HAE must be categorized with respect to severity. In order to characterize the event as severe, all 3 criteria below must be met:

- 1. The participant was unable to treat him/herself. Neurologic impairment, and not the age of the participant, is the explanation for why the participant could not treat him/herself and required the assistance of another person.
- 2. The participant exhibited at least 1 of the following neurological symptoms:
 - Memory loss;
 - Confusion;
 - Uncontrolled behavior;
 - Irrational behavior;
 - Unusual difficulty in awakening;
 - Suspected seizure;
 - Seizure;
 - Loss of consciousness.

3. Either:

- If blood glucose was measured and was ≤54 mg/dL (2.7 mmol/L) using glucometer (or laboratory); or
- If blood glucose was not measured, the clinical manifestations were reversed by oral carbohydrates, subcutaneous glucagon, or IV glucose.

Events that do not meet all the criteria above for severe HAE are characterized as mild or moderate in severity.

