- 13. Previous administration with an IP (drug or vaccine) within 30 days (or as determined by the local requirement) or 5 half-lives preceding the first dose of study intervention used in this study (whichever is longer). Investigational products are prohibited within 14 days plus 5 half-lives prior to the dose of study intervention.
- 14. Known prior participation (ie, received at least 1 dose of study intervention) in a study involving PF-07081532 or known intolerance to a GLP-1R agonist.

Diagnostic Assessments:

- 15. At Screening (S1), standard 12-lead ECG that demonstrates a clinically relevant abnormality that requires further diagnostic evaluation or intervention (eg, new, clinically relevant arrhythmia, conduction disturbance, findings suggestive of ischemia). A potential participant whose pre-dose ECG (on Day 1, 0 hour) demonstrates a clinically relevant abnormality that requires further diagnostic evaluation or intervention will be considered a screen failure.
- 16. A positive drug test at Screening (S1). However, participants in **Groups 2-4**, only, who have been medically prescribed medications, eg. opiates, opioids, cannabinoids, benzodiazepines, methylphenidate (or similar), and report the use of these drugs to the investigator at the screening visit may be allowed to participate, after approval from the sponsor, and if in line with protocol specifications regarding prohibited medications (see Section 6.9, Appendices 9 and 10).
 - **NOTE:** Repeat drug testing to assess study eligibility is **not** permitted in this study.
- 17. At screening or Day -1, a positive breath alcohol test, as assessed using kits approved by sponsor; for the screening test, a single repeat (which may be on a separate day) before Day -1 is permitted to assess eligibility, if needed.
- 18. For females, pregnancy, as indicated by a positive serum pregnancy test at screening and/or positive urine pregnancy test in WOCBP at Day -1.
- 19. Participants with ANY of the following abnormalities in clinical laboratory tests at Screening (S1), as assessed by the study-specific local laboratory and confirmed by a single repeat test, if deemed necessary:
 - Total bilirubin level ≥1.5 × ULN; participants with a history of Gilbert's syndrome may have direct bilirubin measured and would be eligible for this study provided the direct bilirubin level is ≤ ULN.
 - Fasting C-peptide < 0.8 ng/mL.

- FPG >270 mg/dL (15 mmol/L).

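### The glucose limit for a severe hypoglycaemic event differs between its two units: 54 mg/dL is not 2.7 mmol/L

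*Protocol*

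**What the plan says.** Protocol section 8.3.4.2 defines an HAE and requires each one to be given a severity. For severe, the rule is "In order to characterize the event as severe, all 3 criteria below must be met". In outline, criterion 1 is that neurologic impairment left the participant needing another person's help, and criterion 2 is at least one neurological symptom from a list. Criterion 3 has two limbs. The limb for a measured glucose is "If blood glucose was measured and was ≤54 mg/dL (2.7 mmol/L) using glucometer (or laboratory); or". The other limb covers events with no measurement and turns on reversal after treatment. The section closes with "Events that do not meet all the criteria above for severe HAE are characterized as mild or moderate in severity".

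Glucose is printed in both units in two other settings:

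- The three HAE definitions in section 8.3.4.2 all pair 70 mg/dL with 3.9 mmol/L, for example "a glucose value of <70 mg/dL (3.9 mmol/L) using either glucometer (fingerstick blood glucose) at the study site".
- Exclusion criterion 19 in section 5.2.1, repeated in the synopsis, pairs a fasting plasma glucose of 270 mg/dL with 15 mmol/L.

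The fingerstick procedure in section 8.3.4.1 is written in mg/dL only, beginning "If an FSBG result is <70 mg/dL". The 54 mg/dL limit appears nowhere else in the protocol or the SAP.

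**The concern.** A threshold printed in two units should be one concentration, so that the classification does not depend on which unit the assessor reads. Here the mmol/L figure is the stricter one. Because all three criteria are needed, an event that meets criteria 1 and 2 and has a glucose between the two figures changes class with the unit.

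Hypoglycaemia is a listed risk in section 2.3.1, which notes that it increases when drugs of this class are combined with insulin or sulfonylureas. Section 6.9 permits insulin, with dose adjustment during the inpatient stay. Treatment-emergent AEs are a secondary endpoint. What is at stake is the HAE-specific severity class of an individual event. The primary comparison is not affected.

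**Working it through.** **Inputs** (all from the protocol)

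- Severe HAE limit, section 8.3.4.2: 54 mg/dL and 2.7 mmol/L
- HAE limit, section 8.3.4.2: 70 mg/dL and 3.9 mmol/L
- Fasting plasma glucose exclusion, section 5.2.1: 270 mg/dL and 15 mmol/L

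**Step 1. Factor implied by each pair.** Factor = (mg/dL) ÷ (mmol/L). For the rounding range, each printed figure is moved by half a unit in its last digit, in opposite directions.

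| Pair | Factor | Lowest | Highest |
|---|---|---|---|
| 70 and 3.9 | 17.95 | 69.5/3.95 = 17.59 | 70.5/3.85 = 18.31 |
| 270 and 15 | 18.00 | 269.5/15.5 = 17.39 | 270.5/14.5 = 18.66 |
| 54 and 2.7 | 20.00 | 53.5/2.75 = 19.45 | 54.5/2.65 = 20.57 |

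The first two pairs agree with each other. The third range overlaps neither of them, so rounding does not explain the difference.

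**Step 2. Reproduce the protocol's own mmol/L figures with a factor of 18.**

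- 70/18 = 3.89, which rounds to the printed 3.9
- 270/18 = 15.0, as printed
- 54/18 = 3.0, against a printed 2.7
- In the other direction, 2.7 × 18 = 48.6 mg/dL, against a printed 54

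**Step 3. Size of the gap.** 54 − 48.6 = 5.4 mg/dL, which is 5.4/54 = 10% of the mg/dL figure. In the other unit it is 3.0 − 2.7 = 0.3 mmol/L.

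**Step 4. Dependence on the factor.** Both sound pairs allow any factor from 17.59 to 18.31.

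- 54 mg/dL is then 54/18.31 = 2.95 to 54/17.59 = 3.07 mmol/L.
- 2.7 mmol/L is then 2.7 × 17.59 = 47.5 to 2.7 × 18.31 = 49.4 mg/dL.
- The gap is then 54 − 49.4 = 4.6 to 54 − 47.5 = 6.5 mg/dL, so it never closes.

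**Step 5. Readings affected, at a factor of 18.** Whole mg/dL readings that satisfy ≤54 but exceed 2.7 mmol/L are 49, 50, 51, 52, 53 and 54, six in all. If mmol/L is read to one decimal, 49/18 = 2.72 rounds to 2.7 and meets both limits, while 50/18 = 2.78 rounds to 2.8 and does not. That leaves five readings, 50 to 54.

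**Step 6. Events affected.** The class changes only when criteria 1 and 2 are both met, glucose was measured, and the value lies in this band. If glucose was not measured, the other limb of criterion 3 applies and the mismatch has no effect.

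**The case against.** The arithmetic is hard to dispute, so the case on the other side concerns weight.

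- **The mg/dL figure can be read as the operative one.** Every dual-unit glucose limit puts mg/dL first, the fingerstick steps use mg/dL alone, and the study runs under a US IND with no EudraCT number. On that reading 2.7 is only a wrong gloss. This is plausible, but no section says so. Criterion 3 also accepts a laboratory value, and the documents do not give the laboratory's reporting unit for glucose. Even on this reading the printed pair is wrong.
- **Appendix 3 has a separate intensity scale.** Section 10.3.3 rates every AE by its effect on daily activities and clinical status, without a glucose limit. An event meeting criteria 1 and 2 could be rated severe there at any glucose value, and seriousness does not follow from a severe rating. This narrows the consequence to the HAE-specific class, but leaves that class with two limits.
- **Nothing planned depends on the figure.** The SAP names no summary of HAE severity, plans no formal safety analysis, and summarises AEs under sponsor standards. No dosing or stopping rule cites it. This stands.
- **The event is improbable.** It needs neurologic impairment, a glucose in a narrow band and an assessor using mmol/L, among about 32 participants given a single dose. This also stands. The 10% and the six readings describe the width of the band and do not predict how many events will be affected.

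**Conclusion.** The concern holds and is minor. The two figures in criterion 3 state different concentrations, about 5.4 mg/dL or 0.3 mmol/L apart at a factor of 18, and nothing else in the documents settles which is meant. The mismatch sits in a mandatory classification rule, so it is more than a slip in background text.

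That the figures disagree rests only on the protocol's other two glucose pairs. A practical effect rests on a further assumption, that someone judges a reading in mmol/L. Whether the mismatch reached data capture is unknown, because the HAE CRF page is not among the documents.

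**What to change.** Reconcile the two figures in criterion 3 of Protocol section 8.3.4.2 so that both units give the same concentration. Which level stands is for the sponsor's clinical team, and this review takes no position on it. Then confirm that the HAE CRF page and its completion instructions carry the same value. The cost is one corrected figure in the protocol and one check of the CRF page. The planned PK and safety analyses do not change.

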8.3.5. COVID-19 Specific Assessments

Assessment of risk for, symptoms of, or testing for COVID-19 may be performed at Screening, admission to the CRU, and/or at other times during the study at investigator discretion and according to local site policies.

8.3.6. Pregnancy Testing

A serum pregnancy test is required at screening. Following screening, pregnancy tests may be urine or serum tests, and must have a sensitivity of at least 25 mIU/mL. Pregnancy tests will be performed in WOCBP at the times listed in the SoA. Following a negative pregnancy test result at screening, appropriate contraception must be commenced and a second negative pregnancy test result will be required at the baseline visit prior to the participant's receiving the study intervention. Pregnancy tests will also be done whenever 1 menstrual cycle is missed during the active treatment period (or when potential pregnancy is otherwise suspected) and at the end of the study. Pregnancy tests may also be repeated if requested by IRBs/ECs or if required by local regulations. If a urine test cannot be confirmed as negative (eg, an ambiguous result), a serum pregnancy test is required. In such cases, the participant must be excluded if the serum pregnancy result is positive.

8.4. Adverse Events, Serious Adverse Events, and Other Safety Reporting

The definitions of an AE and an SAE can be found in Appendix 3.

AEs may arise from symptoms or other complaints reported to the investigator by the participant (or, when appropriate, by a caregiver, surrogate, or the participant's legally authorized representative), or they may arise from clinical findings of the investigator or other healthcare providers (clinical signs, test results, etc).

The investigator and any qualified designees are responsible for detecting, documenting, and recording events that meet the definition of an AE or SAE and remain responsible to pursue and obtain adequate information both to determine the outcome and to assess whether the event meets the criteria for classification as an SAE or caused the participant to discontinue the study (see Section 7.1).

During the active collection period as described in Section 8.4.1, each participant will be questioned about the occurrence of AEs in a nonleading manner.

In addition, the investigator may be requested by Pfizer Safety to obtain specific follow-up information in an expedited fashion.

8.4.1. Time Period and Frequency for Collecting AE and SAE Information

The time period for actively eliciting and collecting AEs and SAEs ("active collection period") for each participant begins from the time the participant provides informed consent, which is obtained before undergoing any study-related procedure and/or receiving study intervention), through and including a minimum of 28 calendar days, except as indicated below, after the last administration of the study intervention.

Follow-up by the investigator continues throughout the active collection period and until the AE or SAE or its sequelae resolve or stabilize at a level acceptable to the investigator.

When a clinically important AE remains ongoing at the end of the active collection period, follow-up by the investigator continues until the AE or SAE or its sequelae resolve or stabilize at a level acceptable to the investigator and Pfizer concurs with that assessment.

For participants who are screen failures, the active collection period ends when screen failure status is determined.

If the participant withdraws from the study and also withdraws consent for the collection of future information, the active collection period ends when consent is withdrawn.

If a participant permanently discontinues or temporarily discontinues study because of an AE or SAE, the AE or SAE must be recorded on the CRF and the SAE reported using the CT SAE Report Form.

Investigators are not obligated to actively seek information on AEs or SAEs after the participant has concluded study participation. However, if the investigator learns of any SAE, including a death, at any time after a participant has completed the study, and they consider the event to be reasonably related to the study intervention, the investigator must promptly report the SAE to Pfizer using the CT SAE Report Form.

8.4.1.1. Reporting SAEs to Pfizer Safety

All SAEs occurring in a participant during the active collection period as described in Section 8.4.1 are reported to Pfizer Safety on the CT SAE Report Form immediately upon awareness and under no circumstance should this exceed 24 hours, as indicated in Appendix 3. The investigator will submit any updated SAE data to the sponsor within 24 hours of its being available.

8.4.1.2. Recording Nonserious AEs and SAEs on the CRF

All nonserious AEs and SAEs occurring in a participant during the active collection period, which begins after obtaining informed consent as described in Section 8.4.1, will be recorded on the AE section of the CRF.

The investigator is to record on the CRF all directly observed and all spontaneously reported AEs and SAEs reported by the participant.

As part of ongoing safety reviews conducted by the sponsor, any nonserious AE that is determined by the sponsor to be serious will be reported by the sponsor as an SAE. To assist in the determination of case seriousness, further information may be requested from the investigator to provide clarity and understanding of the event in the context of the clinical study.

Reporting of AEs and SAEs for participants who fail screening are subject to the CRF requirements as described in Section 5.4.

8.4.2. Method of Detecting AEs and SAEs

The method of recording, evaluating, and assessing causality of AEs and SAEs and the procedures for completing and transmitting SAE reports are provided in Appendix 3.

Care will be taken not to introduce bias when detecting AEs and/or SAEs. Open-ended and nonleading verbal questioning of the participant is the preferred method to inquire about AE occurrences.

8.4.3. Follow-Up of AEs and SAEs

After the initial AE or SAE report, the investigator is required to proactively follow each participant at subsequent visits/contacts. For each event, the investigator must pursue and obtain adequate information until resolution, stabilization, the event is otherwise explained, or the participant is lost to follow-up (as defined in Section 7.3).

In general, follow-up information will include a description of the event in sufficient detail to allow for a complete medical assessment of the case and independent determination of possible causality. Any information relevant to the event, such as concomitant medications and illnesses, must be provided. In the case of a participant death, a summary of available autopsy findings must be submitted as soon as possible to Pfizer Safety.

Further information on follow-up procedures is provided in Appendix 3.

8.4.4. Regulatory Reporting Requirements for SAEs

Prompt notification by the investigator to the sponsor of an SAE is essential so that legal obligations and ethical responsibilities toward the safety of participants and the safety of a study intervention under clinical investigation are met.

The sponsor has a legal responsibility to notify both the local regulatory authority and other regulatory agencies about the safety of a study intervention under clinical investigation. The sponsor will comply with country-specific regulatory requirements relating to safety reporting to the regulatory authority, IRBs/ECs, and investigators.

Investigator safety reports must be prepared for SUSARs according to local regulatory requirements and sponsor policy and forwarded to investigators as necessary.

An investigator who receives SUSARs or other specific safety information (eg, summary or listing of SAEs) from the sponsor will review and then file it along with the SRSD(s) for the study and will notify the IRB/EC, if appropriate according to local requirements.

8.4.5. Environmental Exposure, Exposure During Pregnancy or Breastfeeding, and Occupational Exposure

Environmental exposure, occurs when a person not enrolled in the study as a participant receives unplanned direct contact with or exposure to the study intervention. Such exposure may or may not lead to the occurrence of an AE or SAE. Persons at risk for environmental exposure include healthcare providers, family members, and others who may be exposed. An environmental exposure may include EDP, EDB, and occupational exposure.

Any such exposures to the study intervention under study are reportable to Pfizer Safety within 24 hours of investigator awareness.

8.4.5.1. Exposure During Pregnancy

An EDP occurs if:

- A female participant is found to be pregnant while receiving or after discontinuing study intervention.
- A male participant who is receiving or has discontinued study intervention inseminates a female partner.
- A female nonparticipant is found to be pregnant while being exposed or having been exposed to study intervention because of environmental exposure. Below are examples of environmental EDP:
- A female family member or healthcare provider reports that she is pregnant after having been exposed to the study intervention by ingestion.

The investigator must report EDP to Pfizer Safety within 24 hours of the investigator's awareness, irrespective of whether an SAE has occurred. The initial information submitted should include the anticipated date of delivery (see below for information related to termination of pregnancy).

• If EDP occurs in a participant/participant's partner, the investigator must report this information to Pfizer Safety on the CT SAE Report Form and an EDP Supplemental Form, regardless of whether an SAE has occurred. Details of the pregnancy will be collected after the start of study intervention and until 28 days after the last dose.

• If EDP occurs in the setting of environmental exposure, the investigator must report information to Pfizer Safety using the CT SAE Report Form and EDP Supplemental Form. Since the exposure information does not pertain to the participant enrolled in the study, the information is not recorded on a CRF; however, a copy of the completed CT SAE Report Form is maintained in the investigator site file.

Follow-up is conducted to obtain general information on the pregnancy and its outcome for all EDP reports with an unknown outcome. The investigator will follow the pregnancy until completion (or until pregnancy termination) and notify Pfizer Safety of the outcome as a follow-up to the initial EDP Supplemental Form. In the case of a live birth, the structural integrity of the neonate can be assessed at the time of birth. In the event of a termination, the reason(s) for termination should be specified and, if clinically possible, the structural integrity of the terminated fetus should be assessed by gross visual inspection (unless preprocedure test findings are conclusive for a congenital anomaly and the findings are reported).

Abnormal pregnancy outcomes are considered SAEs. If the outcome of the pregnancy meets the criteria for an SAE (ie, ectopic pregnancy, spontaneous abortion, intrauterine fetal demise, neonatal death, or congenital anomaly in a live-born baby, a terminated fetus, an intrauterine fetal demise, or a neonatal death), the investigator should follow the procedures for reporting SAEs.

Additional information about pregnancy outcomes that are reported to Pfizer Safety as SAEs follows:

- Spontaneous abortion including miscarriage and missed abortion should be reported as an SAE;
- Neonatal deaths that occur within 1 month of birth should be reported, without regard to causality, as SAEs. In addition, infant deaths after 1 month should be reported as SAEs when the investigator assesses the infant death as related or possibly related to exposure to the study intervention.

Additional information regarding the EDP may be requested by the sponsor. Further follow-up of birth outcomes will be handled on a case-by-case basis (eg, follow-up on preterm infants to identify developmental delays). In the case of paternal exposure, the investigator will provide the participant with the Pregnant Partner Release of Information Form to deliver to his partner. The investigator must document in the source documents that the participant was given the Pregnant Partner Release of Information Form to provide to his partner.

